### 5.8.11 Spirometry

Spirometry is performed at all scheduled visits except Visit 2 (Randomization/ Day 1). Two spirometry assessments are performed at Visit 1 (Screening). For each test, the best values for 12 parameters are provided: Forced Expiratory Volume in 1 Second (FEV1) (L), Forced Vital Capacity (FVC) (L), percent-predicted FEV1 (%), percent-predicted FVC (%), FEV1/FVC, Predicted FEV1 (L), Predicted FVC (L), Peak Expiratory Flow (L/s), Forced Expiratory Flow 25-75% (FEF) (L/s), Forced Expiratory Flow 25% (FEF)

(L/s), Forced Expiratory Flow 50% (FEF) (L/s) and Forced Expiratory Flow 75% (FEF) (L/s).

The following endpoints are defined:

- Absolute value, absolute change and percent change in FEV1 and FVC from baseline at any post-baseline analysis visit (up to EOS);
- Occurrence of treatment-emergent decrease in FEV1 or FVC of > 15% from baseline values at any post-baseline analysis visit.

The analysis visits are defined in Section 11.1.1 ‘Analysis visits’. Absolute value, absolute change and percentage change are calculated for all parameters as defined in Section 11.

The occurrence of treatment emergent abnormalities is assessed at each post-baseline analysis visit for FEV1 (L) and FVC (L), on the value of the percent change from baseline as a decrease greater than 15%.

#### **5.8.12 Optical coherence tomography test**

The optical coherence tomography test (OCT) is performed at Visit 1 (Screening) and Visit 6 (EOT). The presence/ absence of any abnormality (i.e., Yes/No) and whether the finding is clinically significant is recorded in the eCRF.

#### **5.8.13 Ophthalmological examination**

Ophthalmological examinations are performed at each visit except Visit 2 (Randomization/ Day 1). The presence/ absence of any abnormality (i.e., Yes/No) and whether the finding is clinically significant is recorded in the eCRF.

#### **5.8.14 Physical examination**

A complete physical examination is performed at Visit 1 (Screening) and Visit 6 (EOT). A symptom-driven, abbreviated physical examination is performed at all other visits.

The observations are reported according to body system in the eCRF as either normal or abnormal, and whether the finding is clinically significant.

### **5.9 Quality of life variables**

The SF-36v2TM questionnaire is used to assess the subject’s quality of life. The SF-36v2TM is completed by the subject at Visit 2 (Randomization/ Day 1) and at Visit 6 (EOT).

The following endpoint is defined:

- Change in SF-36v2TM Health Survey domain and component scores from baseline to EOT

Full details of the derivations of the raw and norm-based domain scores and physical and mental component scores, and handling of missing data, are described in Section 11 and Appendix 15.2.

## 6 DEFINITION OF PROTOCOL DEVIATIONS

This section refers to all protocol deviations as recorded in a database according to the specifications provided in the protocol violations code list. They are categorized as:

- Important protocol deviations
  - Protocol deviation at screening before randomization
  - Protocol deviation for eligibility criteria at screening (only for randomized subjects)
  - Protocol deviation after randomization
- Minor protocol deviations

Deviations that lead to exclusion of subjects from the Per-protocol set are described in Section 7.1.3 and in more detail in Section 11.2.3.

## 7 ANALYSIS SETS

### 7.1 Definitions of analysis sets

#### 7.1.1 Screened analysis set

The screened analysis set (SCR) includes all subjects who were screened and received a subject number.

#### 7.1.2 Full analysis set

[figure not shown]
The full analysis set (FAS) includes all subjects randomized to a study treatment. In order to adhere to the intention-to-treat (ITT) principle as far as possible:

[figure not shown]
- Subjects are evaluated according to the study treatment to which they were randomized (which may be different from the study treatment they have received).

#### 7.1.3 Per-protocol analysis set

The Per-Protocol Set (PPS) comprises data from all subjects included in the FAS without relevant deviations which could affect the evaluation of the PD parameters (lymphocyte count) and the exploratory disease activity parameters (SLEDAI-2K, PGA).

The protocol deviations leading to exclusion from the PPS are listed in the below table.

Please note:

- If a subject is excluded from the PDS then he is also excluded from the PPS.  
*Rationale:* Insufficient pharmacodynamic effect is unlikely to show e.g. clinical improvement, but will confound the results.
- [REDACTED] If a subject presents with such protocol deviation (specifically, pregnancy test not performed 3 weeks apart), but no pregnancy occurred and all subsequent pregnancy tests were consistently negative during the trial, the subject can be included into the PPS.  
*Rationale:* Biologically this subject is not different from included subjects. However, an important protocol deviation has to be reported.
- [REDACTED]: If a subject presents with such protocol deviation, but the change of the immunologically active medication occurred at or after EOT, the subject can be included in the PPS.  
*Rationale:* The primary endpoint compares the change from baseline to EOT.

#### 7.1.4 Safety analysis set

The safety analysis set (SAF) includes all subjects who received at least one dose of study treatment. Unless otherwise stated, any analysis using the SAF uses all available safety data up to EOS.

Subjects are analyzed based on treatment actually received.

#### 7.1.5 Other analysis sets

##### 7.1.5.1 Pharmacodynamic Analysis Set

The Pharmacodynamics Analysis Set (PDS) includes all subjects who received at least 21 days of study treatment, with lymphocyte count measurements at baseline and post-baseline (namely, one sample taken at least 21 days after the first study treatment intake and no later than 7 days after the last study treatment intake with no treatment interruption documented in the first 21 days).

Subjects are analyzed according to the treatment received.

##### 7.1.5.2 Pharmacokinetic Analysis Set

The pharmacokinetic analysis set (PKS) includes all randomized subjects who received at least one dose of ACT-334441 and provided at least one blood sample for PK evaluation.

Subjects are analyzed based on treatment received.

#### 7.2 Usage of the analysis sets

Overall summary of study disposition, screening failures and including reasons for screening failure are summarized using the SCR.

Overview of analysis sets, study completion/discontinuation, protocol deviations, demographics and baseline disease characteristics, medical history and previous/concomitant medications are summarized for the FAS. Demographics and baseline disease characteristics are also summarized on the PDS.

Study treatment completion/discontinuation, treatment exposure, safety and quality of life are summarized using the SAF.

For pharmacodynamics (PD), the main and supportive analyses are performed on the PDS, FAS and PPS. All other analyses (exploratory disease activity, exploratory biomarkers) are performed on the FAS and on the PPS.

The PKS is used for the analyses of the PK endpoints.

Listings are prepared using the SCR, unless otherwise specified.

**Table 9** provides an overview of the analysis set usage for the main variables of the study.

**Table 9      Overview of the different analysis sets and their usage**

| Analyses/ Data Displays              | Screened analysis set
(SCR) | Full analysis set
(FAS) | Safety Analysis Set
(SAF) | Per-protocol Analysis set
(PPS) | Pharmacodynamics Analysis set
(PDS) | Pharmacokinetics Analysis set
(PKS) |
|--------------------------------------|--------------------------------|----------------------------|------------------------------|------------------------------------|--|--|
| Subject disposition                  | ✓                              | ✓                          | (✓)                          |                                    |  |  |
| Protocol deviations                  |                                | ✓                          |                              |                                    |  |  |
| Analysis sets                        |                                | ✓                          |                              |                                    |  |  |
| Demographic characteristics          |                                | ✓                          | (✓)                          |                                    | ✓                                      |  |
| Baseline disease characteristics     |                                | ✓                          |                              |                                    | ✓                                      |  |
| Medical history                      |                                | ✓                          |                              |                                    |  |  |
| Previous and concomitant medications |                                | ✓                          |                              |                                    |  |  |
| Treatment exposure/compliance        |                                | ✓                          | ✓                            |                                    |  |  |
| Main PD endpoints                    | ✓                              |                            |                              | ✓                                  | ✓                                      |  |
| Other PD endpoints                   | ✓                              |                            |                              |                                    |  |  |
| Safety                               |                                |                            | ✓                            |                                    |  |  |
| Pharmacokinetic variables            |                                |                            |                              |                                    |  | ✓                                      |
| -Exploratory disease activity        | ✓                              |                            |                              | ✓                                  |  |  |
| Quality of life                      |                                |                            | ✓                            |                                    |  |  |
| Exploratory biomarkers               | ✓                              | ✓                          | ✓                            |                                    |  |  |

## 8 DEFINITION OF SUBGROUPS

Not applicable as no subgroups were defined in the protocol. Due to the small number of subjects per dose it was decided that subgroups would not be explored in the CSR SAP.

## 9 GENERAL STATISTICAL METHODOLOGY

This section describes in general terms the statistical models and methods applied.

### 9.1 Statistical methods for binary data

#### 9.1.1 Confidence interval for a proportion

*Statistical considerations.*

For proportions, two-sided  $(1-\alpha)\%$  Clopper-Pearson Confidence Intervals (CIs) [Clopper 1934] are calculated.

*SAS Code*

The Clopper-Pearson CIs are calculated using SAS code similar to:

```
data events;
  set events; * containing - for each group - numbers of subjects (n) and 'events' (e);
  p=round(100*e/n);
  lo=round(100*betainv(.025, e, n-e+1));
  up=round(100*betainv(.975, e+1, n-e));
  if lo=. then lo=0;
  if up=. then up=100;
run;
```

### 9.2 Statistical methods for continuous data

#### 9.2.1 Multiple Comparison Procedure and Modeling (MCP-Mod) approach

Dose-response data are analyzed using the MCP-Mod approach [Bretz 2005]. In brief, this methodology consists of two steps:

1. Multiple Comparisons Procedures (MCP) step to establish a dose-response signal (i.e., the dose-response curve is not flat) using multiple comparison procedures.
2. Modeling (Mod) step to estimate the dose-response curve and target doses using modeling techniques.

[figure not shown]
In this study five models have been pre-specified in the protocol for consideration in all MCP-Mod analyses:  $E_{max}$  (with three different starting values for ED50), quadratic, and sigmoidal  $E_{max}$ . See [Table 10](#) for the parameterization of the dose-response models and [Figure 2](#) as illustration of their basic shapes. The initial values for the parameters are needed in the MCP step of the procedure. They will be estimated in the Mod step based on the actual data.

**Table 10 Parameterization of Models considered in MCP-Mod analyses**

| Model          | Response*                                       | Initial value(s) for parameters |
|----------------|---|---------------------------------|
| Emax           | $E0 + Emax \cdot dose / (ED_{50} + dose)$       | $ED_{50} = 0.2$                 |
| Emax           | $E0 + Emax \cdot dose / (ED_{50} + dose)$       | $ED_{50} = 0.4$                 |
| Emax           | $E0 + Emax \cdot dose / (ED_{50} + dose)$       | $ED_{50} = 1.0$                 |
| Quadratic      | $E0 + beta1 \cdot dose + beta2 \cdot dose^2$    | $beta2/beta1 = -0.167$          |
| Sigmoidal Emax | $E0 + Emax \cdot dose^h / (ED_{50}^h + dose^h)$ | $ED_{50}=0.4, h=1.829$          |

\*Dose = 0, 0.5, 1.0, 2.0 and 4.0

**Figure 2 Dose-response curves considered in MCP-Mod procedure**

The null hypothesis of 'no dose-response' will be rejected if at least one of the five multiple comparison tests has an adjusted p-value  $< 0.05$ . All statistically significant models (i.e., with a multiplicity adjusted p-value  $< 0.05$ ) are fitted in the Mod step and for each model Akaike's Information Criterion (AIC) is calculated. The smaller the value of AIC (= model deviance + 2 times the number of model parameters), the better the fit. The analysis is performed using the R-package *DoseFinding* [Bornkamp 2016].

The basic R-code is similar to:

```
library(DoseFinding)
doses <- c(0, 0.5, 1.0, 2.0, 4.0)
s <- sEmax(ed50=0.4, ed95=2)
candMod <- Mods(
  emax = c(0.2, 0.4, 1.0),
  sigEmax = s,
  quadratic = -0.167,
  doses = doses,
  placEff = 0,
  maxEff = -70% reduction from of the mean baseline value,
  direction = "decreasing"
)
MMfit <- MCPMod(
  dose = TRTDOSEP,
  resp = CHG,
  data = LYM,
  addCovars = ~BASE,
  models = candMod,
  delta = -1.4(arbitrary to run model, target dose not estimated)
)
```

In the *Mods* function call the candidate models are specified, together with the assumed placebo and maximum effects. In the call to the *MCPMod* function, LYM is a data frame with objects TRTDOSEP (Planned Dose for Period 01), CHG (for Absolute change from baseline), and BASE (for Baseline Value) and delta is a target difference vs. placebo. The object *MMfit* is summarized to obtain the MCP test, parameter estimates, target dose and AIC. These elements go in a summary table. The object is plotted to display the fitted dose-response curves.

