### 11.4.2.3 *Main analysis*

The MCP-Mod approach consists of a set of optimized contrast tests for establishing the existence of dose-response effects. The overall strategy is described as follows:

Definition of a set of likely dose-response relations [see Section 11.6 for more details] (the method allows for characteristics of the curve, such as maximum effect, to be defined at doses not studied):

- Maximum effect ( $E_{\max}$ ) with 50% of the maximum effect at dose 0.2 mg
- $E_{\max}$  with 50% of the maximum effect at dose 0.4 mg
- $E_{\max}$  with 50% of the maximum effect at dose 1.0 mg
- Quadratic with maximum effect at dose 3.0 mg (only if the 4 gm dose is studied)
- Sigmoid- $E_{\max}$  with 50% of the maximum effect at dose 0.4 mg and 95% of the maximum effect at dose 2.0 mg.

The existence of dose-response effects will be assessed with the optimized contrast tests. Dose-response effects are established at one-sided level  $\alpha=5\%$ , if the following condition on the  $p$  value holds for at least one contrast  $i$ :  $p_i := 1 - F_{\Sigma_{\text{Dunnnett}}}(Z_i) < 0.05$ , where  $F_{\Sigma_{\text{Dunnnett}}}$  describes the Dunnnett-distribution with correlation matrix  $\Sigma_{\text{Dunnnett}}$ .

The model with the minimum  $p$ -value will be fitted to the data. As a sensitivity analysis, all remaining significant models will be fitted to the data, and model-based dose estimates will be calculated.

Given established dose-response effects with MCP-Mod, PD effects will be analyzed based on pairwise comparisons of reduction in lymphocyte count from baseline for each active dose levels to placebo using an analysis of covariance (ANCOVA) model, adjusted for baseline lymphocyte counts. Testing will be done with two-sided significance level 5%. The type-1 error will be controlled via a hierarchical ordering of the tests: pairwise comparison will be conducted in decreasing dose order.

The dose-response data will be summarized with point-wise and model-based estimates, standard deviation and 95% confidence-intervals (CI) on the reduction in lymphocytes from baseline at the examined dose levels. A plot of the estimated dose-response curve with 95% credibility interval limits will be presented along with the observed response at each dose.

This analysis will be performed on the PDS.

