### 10.6.3 Main analysis

The MCP-Mod approach consists of a set of optimized contrast tests for establishing the existence of dose-response effect. The overall strategy is described as follows:

Definition of a set of likely dose-response relations (the method allows for characteristics of the curve, such as maximum effect, to be defined at doses not studied):

- Maximum effect ( $E_{max}$ ) with 50% of the maximum effect at dose 0.2 mg

- $E_{max}$  with 50% of the maximum effect at dose 0.4 mg
- $E_{max}$  with 50% of the maximum effect at dose 1.0 mg
- Quadratic with maximum effect at dose 3.0 mg
- Sigmoid- $E_{max}$  with 50% of the maximum effect at dose 0.4 mg and 95% of the maximum effect at dose 2.0 mg.

The existence of dose-response effects is assessed with the optimized contrast tests. Dose-response effects are established at one-sided level  $\alpha=5\%$ , if the following condition on the  $p$  value holds for at least one contrast  $i$ :  $p_i := 1 - F_{\Sigma_{Dunnett}}(Z_i) < 0.05$ , where  $F_{\Sigma_{Dunnett}}$  describes the Dunnett-distribution with correlation matrix  $\Sigma_{Dunnett}$ .

The model with the minimum p-value is fitted to the data. As a sensitivity analysis, all remaining significant models are fitted to the data, and model-based dose response estimates are calculated. A table summarizing the t-statistic and adjusted p-value for each curve is presented by decreasing adjusted p-value.

A plot of the estimated dose-response curve with 95% CIs is presented along with the observed response at each dose. A table summarizing the estimates (and standard error) of each dose-response curve parameters and the AIC will also be presented.

Given established dose-response effects with MCP-Mod, PD effects are analyzed based on pairwise comparisons of reduction in lymphocyte count from baseline to EOT for each active dose level to placebo using an analysis of covariance (ANCOVA) model, adjusted for baseline lymphocyte count. Testing is done with two-sided significance level 5%. The type-1 error is controlled via a hierarchical ordering of the tests: pairwise comparison is conducted in decreasing dose order. The analysis described in this paragraph is repeated for the % change from baseline to EOT in lymphocyte counts.

This analysis is performed on the PDS.

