#### *Treatment variables*

**Randomization Number** is extracted from the DS domain, from the Reference ID variable, for records with a Standardized Disposition Term equal to RANDOMIZED.

**Planned Arm Code, Description of Planned Arm, Actual Arm Code and Description of Actual Arm** are retrieved from the DM domain.

The actual treatment variables are derived similarly to the planned treatment variables according to the following table:

| Planned Arm Code | Description of Planned Arm | Planned Treatment for Period 01 (N) | Planned Treatment for Period 01 | Planned Dose for Period 01 |
|------------------|----------------------------|-------------------------------------|---------------------------------|----------------------------|
| A                | ACT-334441 0.5mg           | 2                                   | ACT-334441 0.5 mg               | 0.5                        |
| B                | ACT-334441 1.0 mg          | 3                                   | ACT-334441 1.0 mg               | 1.0                        |
| C                | ACT-334441 2mg             | 4                                   | ACT-334441 2.0 mg               | 2.0                        |
| D                | Placebo Control (Part A)   | 1                                   | Placebo                         | 0                          |
| E                | ACT-334441 4mg             | 5                                   | ACT-334441 4.0 mg               | 4.0                        |
| F                | Placebo Control (Part B)   | 1                                   | Placebo                         | 0                          |

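### SAP 9.2.1 conflicts with the SAP's own rules in two places: it uses planned dose in the as-treated main MCP-Mod analysis, and it both disclaims and tabulates a target dose

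*SAP*

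**What the plan says.** **Dose variable.** SAP 9.2.1 sets the dose argument of the MCP-Mod call to TRTDOSEP, and the explanatory text repeats the choice: "LYM is a data frame with objects TRTDOSEP (Planned Dose for Period 01". SAP 10.6.3 says of the main analysis: "This analysis is performed on the PDS". SAP 7.1.5.1 fixes how that set is handled: "Subjects are analyzed according to the treatment received". The FAS follows the opposite rule in SAP 7.1.2: "Subjects are evaluated according to the study treatment to which they were randomized". SAP 10.6.4 repeats MCP-Mod on the FAS. Actual-dose variables are available, because SAP 11.2.2 states: "The actual treatment variables are derived similarly to the planned treatment variables according to the following table".

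**Target dose.** The code in SAP 9.2.1 contains "delta = -1.4(arbitrary to run model, target dose not estimated". The paragraph after it describes delta as a target difference from placebo and lists among the outputs "parameter estimates, target dose and AIC. These elements go in a summary table". The opening of 9.2.1 also gives target doses as an aim of the modelling step. SAP 10.6.3 lists the tables actually planned: test statistics, adjusted p-values, curve parameters with standard errors, and AIC. It lists no target dose.

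**The concern.** The trial has two MCP-Mod runs that are meant to differ in how dose is assigned: as treated on the PDS and as randomised on the FAS. As coded, both would assign the planned dose, so the main run would not follow the rule of its own analysis set. If a PDS subject took the wrong dose, that subject's lymphocyte change would be modelled at a dose not taken.

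On the second point, a programmer cannot satisfy both instructions. Following the text would put a dose in the main results table that answers to an effect size the SAP itself calls arbitrary. A reader could take that figure as a dose recommendation, since Protocol 1.4 hopes that the study may help to choose doses for later trials.

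**Working it through.** **1. The plan's own figures.** Inputs from Protocol 11.6.1: baseline 2.0 x10^9/L, maximum reduction 70%, SD 0.45, 12 subjects per active dose, 16 on placebo, 10% excluded from the PDS. The candidate curves are in SAP 10.6.3.
- Delta: 0.70 x 2.0 = 1.4.
- Quadratic with its peak at 3 mg: ratio = -1/(2 x 3) = -0.167.
- Sigmoid with 50% at 0.4 mg and 95% at 2 mg: (2/0.4)^h = 0.95/0.05 = 19, so h = ln 19/ln 5 = 1.829.
- Pairwise power for a 25% reduction (0.25 x 2.0 = 0.5): 77.3% with n = 10.8 and 14.4 and pooled df 52. For 70% it is 100%. The protocol states 77% to 100%.
- MCP-Mod power is about 100% for every candidate curve, against at least 90% stated for 64 subjects and at least 80% for 48.

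All of these reproduce, and none depends on either point below.

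**2. Can a mis-dosed subject be in the PDS?** Protocol 5.1.10.8 has a discontinuation rule for mis-dispensing with incorrect intake, and the PDS needs at least 21 days of treatment. But Protocol 5.1.6.3 supplies each subject up to the next scheduled visit, and note 13 to the visit schedule says that nothing is dispensed at Visit 3. An unnoticed wrong kit from Day 1 could thus be taken until about Week 4, that is 28 days, which exceeds 21. The case is narrow but possible.

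**3. Size for one such subject** (illustrative; the subject is assumed to respond as the average for the dose taken).
- Placebo planned, 4 mg taken. Take the 4 mg effect as 1.4 x 4/(0.4 + 4) = 1.27 (Emax curve, ED50 0.4, asymptote 1.4). The pooled placebo mean moves by 1.27/16 = 0.08 x10^9/L, or 1/16 = 6% of the effect.
- 4 mg planned, placebo taken, true effect 1.4. The 4 mg mean moves by 1.4/12 = 0.12 or 1.4/11 = 0.13 x10^9/L, or 8% to 9% of the effect.

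Both errors pull the 4 mg versus placebo difference towards zero. With no mis-dosed PDS subject the shift is 0.

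**4. Does delta or the assumed maximum effect matter to the test?** The optimal contrast for a curve with group means m and sizes n is proportional to n x (m - weighted mean of m), then normalised. Multiplying the whole curve by a constant cancels. The contrasts were identical for maximum effects of 1.4, 1.05 and 0.7. Delta does not enter the test at all; it affects only the target dose.

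**5. Would a 1.4 effect fall within 0 to 4 mg?** The documents do not say, so this needs an assumption. Solved directly:
- If 70% is the largest effect within the studied range, the target dose is exactly 4.0 mg for the Emax and sigmoid curves and 3.0 mg for the quadratic.
- If 70% is the asymptote, the Emax and sigmoid curves never reach 1.4; their effects at 4 mg are 1.12 to 1.38.

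Simulation: 600 trials per scenario, n = 14/11/11/11/11, SD 0.45, minimum-p model fitted, assumed bounds ED50 0.004 to 6 mg and h 0.5 to 10, baseline covariate ignored, baseline 2.0.

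| Assumed truth | Trials with no target dose in 0 to 4 mg |
|---|---|
| 1.4 is the maximum within the range | 44% to 54% |
| 1.4 is the asymptote | 53% to 95% |
| Maximum within the range is 64% (1.28), the Phase 1 upper figure | 74% to 77% |
| Curve running from 34% to 64%, the Phase 1 range | 81% |

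A fixed delta also changes meaning with baseline: at an illustrative mean of 1.5, 1.4/1.5 = 93%.

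**The case against.** SAP Section 9 describes methods in general terms and labels the code as only similar to what will be run. The same code serves the FAS rerun, where planned dose is correct. The explicit rule for the PDS, together with the derived actual-treatment variables, would guide a careful programmer. Mis-dosing that survives into the PDS needs an unusual chain of events. The 4 mg capsules belong to Part B, so a placebo and 4 mg mix-up essentially concerns the 4 Part B placebo subjects or the 12 on 4 mg. All of this stands, and it limits the size of the point. It does not remove the conflict, because the prose as well as the code names the planned dose.

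On the target dose, the comment in the code and SAP 10.6.3 agree that none is planned, so the contrary wording may be a generic leftover. That is plausible, and it is the reason that deletion is the first remedy.

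Three stronger readings are tempting but not supported:
- **That the target dose usually lies outside the studied range.** The share runs from about half to 95% according to the assumption. Protocol 11.6.1 speaks of a 70% maximum for any dose, which reads naturally as an effect at a studied dose; on that reading it is about a coin toss.
- **That the protocol clearly promised a target dose which the SAP dropped without declaring it.** Protocol 11.4.2.3 says "all remaining significant models will be fitted to the data, and model-based dose estimates will be calculated", but it sets no target effect, and the same section speaks of model-based estimates at the doses examined. The matching sentence in SAP 10.6.3 refers to dose-response estimates. The wording is ambiguous, not a clear promise.
- **That delta and the assumed maximum effect disagree unless baseline is 2.0, which spoils the test.** Step 4 of the working shows that it does not.

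**Conclusion.** Both conflicts are in the text and should be corrected. The planned-dose instruction is wrong for the PDS as written. Its effect is nil if every PDS subject took the planned dose, and otherwise roughly 0.08 to 0.13 x10^9/L in a group mean for one subject. Those figures rest on the planning inputs and the two illustrative mix-ups; they are not a forecast. A reader might infer that the main dose-response estimate is contaminated, but the documents show only that it could be.

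The target-dose point is an internal contradiction about one output: the same section says that it is not estimated and that it is tabulated. It has no bearing on the MCP test, the one-sided 5% alpha, the planned power, the curve fits or AIC.

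**What to change.** 1. In SAP 9.2.1, state that the PDS run uses the actual-dose variable and the FAS run uses TRTDOSEP, in both the code and the explanatory text.
2. Delete the target dose from the summary-table sentence in 9.2.1, and align the stated aim of the modelling step with the outputs in 10.6.3. Only if a target dose is wanted, pre-specify a justified delta relative to baseline and say how a target dose beyond 4 mg, or one never reached, is reported. Taking that delta from the reductions in Protocol 1.4 would be a preference, since those figures come from other drugs in multiple sclerosis.

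The cost is one variable name and a few words of SAP text. Sample size, alpha and power do not change.
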